4.1. Features of product

This study involves use of market approved products that will be provided by the Sponsor. Although these products are already market approved to be implanted in patients who meet the indications for use, these products are not approved for use in an MRI environment. Therefore, the study procedure i.e. MRI scan, is considered investigational in nature.

4.2. Structure and composition, operating principle and function mechanism of product

- The Ellipse ICDs are intended to provide ventricular antitachycardia pacing and ventricular defibrillation for automated treatment of life-threatening ventricular arrhythmias. In cases where AF Suppression™ is available, AF Suppression pacing is indicated for suppression of paroxysmal or persistent atrial fibrillation in patients with the above ICD indication and sinus node dysfunction. The Ellipse ICDs are supported by the St. Jude Medical Merlin Patient Care System (Merlin PCS) with software Model 3650, Software Model 3330 v. 20.X (or higher).
- The Quadra Assura MP CRT-D devices are intended to provide ventricular antitachycardia pacing and ventricular defibrillation for automated treatment of life-threatening ventricular arrhythmias, they are also intended to resynchronize the right and left ventricles in patients with congestive heart failure. They are equipped with an IS4-LLLL low voltage connector to facilitate implantation of an IS4 LV four electrode lead. Also, devices with a Q suffix have a high voltage DF4-LLHH bore that allows the use of a high voltage lead with a DF4 connector. The Quadra Assura MP CRT-D devices deliver 40J of energy and are supported by the St. Jude Medical Merlin Patient Care System (Merlin PCS) with software Model 3330 version 16.1.1 (or higher).
- The Durata Models 7120 and 7122Q leads are 7 French, transvenous, steroid eluting, bipolar, DF4 compatible (single connector with four electrical terminals), active fixation leads intended for permanent sensing and pacing of the right ventricle and the delivery of cardioversion/ defibrillation therapy when used with a compatible St. Jude Medical pulse generator with a DF4-LLHH or DF4-LLHO lead receptacle designation.
- The Optisure Model LDA220Q transvenous leads are market released leads indicated for use with compatible pulse generators (refer to the applicable defibrillator manual for system indications). They provide pacing and sensing and deliver cardioversion/ defibrillation therapy to the heart.
- The Tendril STS Model 2088TC pacing lead is a market-released MR conditional active-fixation lead indicated for permanent sensing and pacing of the heart.

- The Isoflex Model 1944 is a J-shaped, market-released, passive-fixation leads indicated for permanent sensing and pacing of the heart.
- The Quartet Models 1456Q, 1458Q, and 1458QL leads are 5.1 French, transvenous, steroid eluting, quadripolar, IS4 compatible (single connector with four electrical terminals), passive fixation leads intended for permanent sensing and pacing of the left ventricle when used with a compatible St. Jude Medical biventricular system with an IS4-LLLL lead receptacle designation.

4.3. Scope of study

This is a study in at least 60 subjects from at least 6 study centers in China who provide consent to have any of the four defibrillation system combination groups implanted (See **Figure 1**), undergo a non-diagnostic MRI scan, and complete follow-up through 1-month post-MRI scan.

5. Indications, contraindications and precautions of product

Please refer to the products Instructions For Use (IFU) for the indications, contraindications, and precautions of each device.

6. Device handling and storage

This study involves use of market approved products; the study procedure i.e. MRI scan, is considered investigational in nature. Device handling and storage should be done according to the Instructions for Use. Due to the devices being supplied by the Sponsor, it is required that they be stored in a secure area to prevent unauthorized access or use.

7. Device accountability

Study system devices will be provided by the sponsor to study sites. The Principal Investigator or an authorized designee must maintain records of device information as defined by sponsor and such study devices can only be used in patients that are enrolled into the study.

The Sponsor will maintain accountability documentation for all used study devices.

8. Overall design

This is a prospective, multi-center, single-arm study to evaluate the safety and effectiveness of the Ellipse VR/DR ICDs, and the Quadra Assura MP CRT-D, with Durata or Optisure defibrillation leads, Tendril STS or Isoflex pacing leads, and the Quartet quadripolar LV lead in a 1.5T MRI environment for MR-conditional labeling expansion in China.

This study will be conducted in at least 6 centers in China and at least 60 subjects who provide consent for participation will be enrolled. Subjects will be considered enrolled after providing consent. Subjects will be implanted with any one of the device/lead combination groups outlined in **Figure 1**, depending on their clinical need as determined by the Investigators. At least 15 subjects will be enrolled in each group.

- **Group 1** will have at least 15 enrolled subjects with the Ellipse VR single-chamber ICD with a Durata lead in the RV.
- **Group 2** will have at least 15 enrolled subjects with the Ellipse DR dual-chamber ICD with a Durata lead in the RV and a Tendril STS lead in the RA.
- **Group 3** will have at least 15 enrolled subjects with the Ellipse DR dual-chamber ICD with a Optisure lead in the RV and a Isoflex lead in the RA.
- **Group 4** will have at least 15 enrolled subjects with a Quadra Assura MP CRT-D and an Optisure or Durata lead in the RV, an Isoflex or Tendril STS lead in the RA, and a Quartet lead in the LV.

The enrollment group and group 4 lead pairing will be at the discretion of the Investigator, dependent on patient needs in conjunction with study needs to fulfill study goals.

At least forty-five (45) days after system implantation or after a system revision, subjects will have a baseline visit followed by an MRI visit; subjects will undergo a study-related MRI scan at 1.5T. Subjects will have a 1-month follow-up after the study MRI scan. The minimum duration of each subject's participation is approximately 2.5 months from enrollment. The expected duration of enrollment is approximately 14 months. The total duration of clinical study is expected to be 16.5 months.

8.1. Clinical study design

8.1.1. Clinical study objective

The objective of this clinical study is to evaluate the safety and effectiveness of the Ellipse VR/DR, implantable cardiac defibrillators (ICDs), and the Quadra Assura MP CRT-Ds, with Durata or Optisure defibrillation leads, Tendril STS or Isoflex pacing leads, and the Quartet quadripolar leads in a 1.5T MRI environment for MR-conditional labeling expansion of these market-approved ICD systems in China.

8.1.2. Selection of clinical study method and rationale

A prospective, multi-center, non-randomized, open-label, single arm clinical study design was chosen to generalize the study results by enrolling subjects across multiple sites and limit the sample size to the minimum number required by the NMPA to receive MR labeling approval. This study intends to provide clinical data from a local Chinese population to supplement IDE clinical data from a population in the United States and

Europe for submission to the NMPA in support of a marketing application of MRI labeling expansion for these ICD/CRT-D systems in China.

The selection of this local clinical study method was based on discussions with the NMPA and the Sponsor during a pre-market workshop meeting held on November 9th and 10th, 2016 in China.

8.1.3. Measures for reducing and avoiding bias

Measures to reduce and avoid bias in this study include: allowing all subjects who meet the eligibility criteria specified in this CIP may be enrolled in this study, the Sponsor will approach sites for participation without bias or consideration for specific demographic subgroups; additionally, clinical events (adverse device effects and deaths) occurring after the MRI settings have been programmed, will be adjudicated by an independent Clinical Events Committee (CEC).

The CEC is an independent adjudication body comprised of qualified physicians who are not participants in the clinical investigation. The CEC will review and adjudicate pre-specified events reported by investigators or identified by Safety personnel for the clinical investigation as defined in the CEC charter and according to definitions provided in this CIP.

8.1.4. Investigational medical device and reference medical device/reference diagnosis/therapeutic method (if any)

Devices and reference numbers are listed in **Table 1: Study Device** above.

8.1.5. Selection of subjects

The study population includes male and female Chinese nationals that meet the eligibility requirements and give consent for the study. Vulnerable subjects, such as minors or those unable to provide consent are excluded from participating.

8.1.6. Inclusion criteria

Assessment for general eligibility criteria is based on medical records of the site and interview with a candidate patient. If some of the clinical and laboratory tests are not included in site standard tests, they must be done but after written informed consent is obtained. Patients must meet ALL the inclusion criteria to be considered for the clinical study. If ANY of the exclusion criteria are met, the patient is excluded from the clinical study and cannot be enrolled.

To participate in this clinical study, the subject must meet all the following inclusion criteria:

- Have an approved indication for implantation of an ICD, or CRT-D
- Be a Chinese national
- Will be implanted with one of the following device/lead combinations evaluated in this study:
 - Group 1: Ellipse VR single-chamber ICD with a Durata lead in the RV
 - Group 2: Ellipse DR dual-chamber ICD, with a Durata lead in the RV and a Tendril STS lead in the RA
 - Group 3: Ellipse DR dual-chamber ICD with a Optisure lead in the RV and a Isoflex lead in the RA
 - Group 4: Quadra Assura MP CRT-D and an Optisure or Durata lead in the RV, an Isoflex or Tendril STS lead in the RA, and a Quartet lead in the LV
- Be willing to undergo an elective MRI scan without sedation \geq 45 days after implant

NOTE: Antianxiety agents (e.g. minor tranquilizers, etc.) may be used as long as the patient can communicate with site personnel during the MRI scan

- Be able to provide informed consent for study participation (legal guardian or legally authorized representative is NOT acceptable)
- Be willing and able to comply with the prescribed follow-up tests and procedures
- Are not contraindicated for an MRI scan (per the MRI Screening Form)
- Subjects who are at least 18 years of age (or older, required by local law)

8.1.7. Exclusion criteria

Subjects who meet any of the following exclusion criteria must be excluded from the clinical investigation:

- Have a competitor's MRI compatible endocardial lead implanted or capped
- Have another existing active implanted medical device, e.g., neurostimulator, infusion pump, etc. that has MR labeling that will not allow the MRI scans per this protocol to be completed.
- Have other non-MRI compatible device or material implanted. The following examples may be included as long as labelling of these devices allow MRI scans conducted per this protocol:
 - MRI compatible knee replacements, hip replacements, stents, etc.
 - MRI compatible mechanical, prosthetic, and bio prosthetic heart valves
 - Non-removable dental implants
- Have a lead extender, adaptor, or capped/abandoned lead
- Enrolled or intend to participate in a clinical drug and/or device study (investigational device, investigational drug, new indication for a device or drug or additional testing beyond standard of care procedures), which could confound the results of this study as determined by Abbott.

- Pregnant or planning to become pregnant during the duration of the subject's participation in the study
- Have a life expectancy of less than 12 months due to any condition

8.1.8. Criteria and procedures for study/study treatment termination

No formal statistical rule for early termination of the clinical study for insufficient effectiveness of the device/ MRI procedures under investigation is defined.

The Sponsor reserves the right to discontinue the clinical study at any stage or reduce the follow-up period with suitable written notice to the investigator. Possible reason(s) may include, but are not limited to:

- Unanticipated adverse device effect (e.g., UADE) occurs and it presents an unreasonable risk to the participating subjects
- Any oversight committee (e.g., Steering/Executive Committee, Data Monitoring Committee) makes a recommendation to stop or terminate the clinical study (such as higher frequency of anticipated adverse device effects)
- Further product development is cancelled

Should the clinical study be discontinued by the Sponsor, subjects will be followed per routine hospital practice with device-related AEs reported to the Sponsor as per vigilance/commercial reporting requirements.

Should this occur, the investigator shall return all clinical investigation materials (including devices) to the Sponsor and provide a written statement as to why the premature termination has taken place to the IRB/EC (if applicable). All applicable clinical study documents shall be subject to the same retention policy as detailed in section **18.1** of the CIP.

A Principal Investigator, IRB/EC or regulatory authority may suspend or prematurely terminate participation in a clinical study at the study sites for which they are responsible. The investigators will follow the requirements specified in the Clinical Trial Agreement.

If the Sponsor suspends or prematurely terminates the clinical study at an individual site in the interest of safety, the Sponsor will inform all other Principal Investigators.

If suspension or premature termination occurs, the Sponsor will remain responsible for providing resources to fulfill the obligations from the CIP and existing agreements for following the subjects enrolled in the clinical study, and the Principal Investigator or authorized designee will promptly inform the enrolled subjects at his/her site, if appropriate.

The clinical study will be concluded when:

- All sites are closed AND
- The final report has been provided to investigators or the Sponsor has provided formal documentation of clinical study closure.

8.1.9. Time of enrollment

The expected duration of enrollment is approximately 14 months.

8.1.10. Anticipated duration of clinical study and the reasons for determination

With an expected duration of enrollment of 14 months, the 45-day post-implant stabilization period, and the 1-month post-MRI scan visit, the total duration of clinical study is expected to be 16.5 months from the time of first enrollment.

8.1.11. Anticipated participation duration of each subject

Each subject is anticipated to participate in this clinical investigation for 2.5 months from the time of enrollment. This accounts for the 45-day post-implant stabilization period and 30 days for completion of the 1-month post-MRI visit.

8.1.12. Number of subjects required for clinical study

A minimum of 60 total subjects will be enrolled in this study. Fifteen (15) subjects for each of the 4 main device groups (See **Figure 1**) will be enrolled in this study to meet the minimum required 10 subjects per device arm, as requested by the NMPA for each group accounting for attrition of anticipated 5 subjects for each group in this study.

8.2. Effectiveness evaluation method

There are two primary effectiveness endpoints to be evaluated in this study.

8.2.1. Description of the effectiveness endpoints

- Proportion of leads with a capture threshold increase of $\leq 0.5V$ at 0.5ms for RA and RV leads and $\leq 1.0V$ at 0.5ms for LV leads from pre-MRI scan to 1-month post-MRI scan testing.
- Proportion leads with a sensing amplitude decrease of $\leq 50\%$ from pre-MRI scan testing to 1-month post-MRI scan.

8.2.2. Selection of method and time for evaluation, recording and analysis of the effectiveness endpoints

Since the objective is to evaluate the effect of MRI exposure for the ICD/ CRT-D device groups included in this study, the effectiveness parameters were selected to compare abnormal changes in device performance from pre- to 1-month post- MRI scan. The pre-MRI measurements are collected within the same day prior to the MRI scan. The 1-month post-MRI scan measurements are collected at 30 days post-MRI scan (within +14 days) to ensure any effect of the MRI exposure is captured.

The effectiveness parameters are recorded directly from the device. The device measurements will be obtained using the Merlin programmer to interrogate the device during study visits. The analysis of the effectiveness parameters will be conducted on all subjects with complete data from pre- to 1-month post-MRI scan.

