8.4.6. Complete system explants

If the subject has the entire study ICD/ CRT-D system removed at any time during the study, and the subject will not receive a replacement study ICD/ CRT-D system, withdraw the subject from the study. Complete a Product Out of Service CRF and submit through EDC. A System Revision CRF is not required to be submitted.

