8.4.7. System revisions

In cases where only the device pocket is revised (leads are not repositioned, leads have not been disconnected from the ICD/ CRT-D), a System Revision CRF is not required to be submitted. A System Revision CRF should be completed for all other types of revisions

such as generator replacement, lead replacement and lead repositioning has been performed.

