8.4.7.2. Revisions after the MRI scan

If a system revision occurs after the MRI scan, then the subject will remain in the study until the subject completes the 1 Month Post Scan visit.

Any explanted devices or leads (including damaged leads, lead segments and lead fragments) should be returned to Abbott promptly for analysis. Document any change to the status of the lead and device (e.g. capped, removed) on the Product Out of Service CRF. Refer to

Table 9: System Revisions Scenarios After MRI Scan below to determine what actions need to be performed.

TABLE 8: SYSTEM REVISIONS SCENARIOS PRIOR TO MRI SCAN

System Revisions that occur prior to MRI Scan	Action	Data Submission

Revisions where the study ICD/ CRT-D system is still implanted:
 
 • Study lead(s) or the ICD/ CRT-D is repositioned or replaced, AND • The study ICD/ CRT-D and study lead(s) are still implanted, AND • No other non-MRI compatible material has been implanted 	
Obtain (if possible):
 
 • In-clinic bipolar and unipolar* capture threshold at a pulse width of 0.5 ms. for the applicable lead(s). Either the manual decrement or automatic (in-clinic, programmer based) method may be used to obtain the capture threshold. • In-clinic bipolar sensing amplitude for the applicable lead(s). Either the incremental or the automatic (in-clinic, programmer based) method may be used to obtain the sensing threshold. • In clinic atrial and ventricular bipolar and unipolar* lead impedance for the applicable lead • Retain the subject in the study. If the MRI scan visit has not occurred yet, then wait at least 45 days from the successful revision before completing the MRI scan visit. If the MRI scan visit has occurred, then follow the subject through the 1 Month Post Scan visit. 
*NOTE: Unipolar and bipolar configurations should be collected for LV leads
	
Complete and submit the appropriate forms to Abbott. Refer to Table 4. It is recommended that the following device printouts and measurements be maintained at the site.
 
 • FastPath Summary • Test Results with Freezes, Include Battery & Leads • Wrap-up Overview with full parameters

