
Revisions where the study ICD/ CRT-D system is still implanted
 
 The study ICD/ CRT-D and study lead(s) are still implanted, BUT A non-MRI compatible material(s) or device(s) has been implanted 
OR
 
Revisions where the study ICD/ CRT-D system is still implanted
 
 Study ICD/ CRT-D and study lead(s) is repositioned or replaced, AND The study ICD/ CRT-D and study lead(s) are still implanted, AND No other non-MRI compatible material has been implanted 	
Obtain (if possible):
 
 In-clinic bipolar and unipolar* capture threshold at a pulse width of 0.5 ms. for the applicable lead(s). Either the manual decrement or automatic (in-clinic, programmer based) method may be used to obtain the capture threshold. In-clinic bipolar sensing amplitude for the applicable lead(s). Either the incremental or the automatic (in-clinic, programmer based) method may be used to obtain the sensing threshold. In clinic bipolar and unipolar* lead pacing impedance for the applicable lead(s) Continue to follow the patient until the subject completes the 1 Month Post scan visit. 
*NOTE: Unipolar and bipolar configurations should be collected for LV leads
	Once required testing has been performed, complete and submit the appropriate forms to Abbott. Refer to Table 4

Revisions where the study lead(s) is not retained
 
 Study lead(s) is replaced with another lead, AND The study ICD/ CRT-D is still implanted, AND 	The subject will be withdrawn from the study.	
Document consenting information (name of the study, date of consent and inclusion/exclusion) in the subject's medical and/or study records.
 
Submit the Pre-MRI CRF, MRI CRF, System Revision CRF and Withdrawal CRF. Submit

System Revisions that occur after the MRI Scan	Action	Data Submission

 • A non-MRI compatible material(s) or device(s) has been implanted 		
Deviation, Product Out of Service, Adverse Event CRFs if applicable.
 
It is recommended that the following device printouts and measurements be maintained at the site.
 
 • FastPath Summary • Test Results with freezes, Include Battery & Leads • Wrap-up Overview with full parameters

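### The visible text lets a lead revised after the scan be scored on its post-revision value, and lets a withdrawn subject's leads drop out, so the effectiveness proportions could read too high

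*Combined protocol and SAP*

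**What the plan says.** Both effectiveness endpoints are proportions of leads, each judged from a pre-scan and a 1-month measurement (CIP 2.2 and 8.2.1; SAP 1.4.2). CIP 8.2.2 sets the analysis set: "The analysis of the effectiveness parameters will be conducted on all subjects with complete data from pre- to 1-month post-MRI scan". SAP 2.9 adds that the reasons for missing primary endpoint data will be summarised to judge whether the gaps could affect results. It names no failure rule and no sensitivity analysis.

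On revisions after the scan, CIP 8.4.7.2 begins: "If a system revision occurs after the MRI scan, then the subject will remain in the study until the subject completes the 1 Month" post-scan visit. It then refers to Table 9 for the action. One Table 9 row covers the case where "Study ICD/ CRT-D and study lead(s) is repositioned or replaced" with the study system still implanted. The instruction there is: "Continue to follow the patient until the subject completes the 1 Month Post scan visit". Another row covers a study lead exchanged for another lead, with the study generator still in place and non-MRI-compatible material implanted. For that row: "The subject will be withdrawn from the study". CIP 8.4.6 also withdraws the subject "If the subject has the entire study ICD/ CRT-D system removed at any time during the study", if no study replacement follows.

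The section foresees leads that end up capped or removed: "Document any change to the status of the lead and device (e.g. capped, removed) on the Product Out of Service CRF".

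The bodies of SAP 2.1 (analysis populations) and the detail under each endpoint in SAP 2.3.2 are redacted.

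**The concern.** A lead revised for loss of capture or sensing is the outcome these endpoints are meant to detect. CIP Table 10 lists such loss, through electrode heating and tissue damage, as a potential MRI-related event. The visible text gives two ways for that lead not to count against the proportion.

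- **Overwritten.** A repositioned lead is measured again at 1 month. Nothing visible stops that value being set against the pre-scan value from the old position, where it may pass. The same could happen to a replaced lead, but only if the analyst pairs the new lead with the old lead's baseline.
- **Dropped.** A withdrawn subject has no 1-month value and falls outside the complete-data set. A lead capped or removed without replacement has none either.

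The two proportions are the main descriptive effectiveness evidence for the labelling submission. Analysis and reporting go group by group (SAP 2.6; CIP section 20), with a required minimum of 10 subjects per group (CIP 8.1.12). One lead is therefore visible in the result.

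**Working it through.** **1. The plan's own figure.** CIP 8.1.12: 10 required + 5 expected attrition = 15 per group, and 4 × 15 = 60. This reproduces. The documents give no power, precision or revision rate, so what follows is an illustration and not an estimate.

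**2. The passages side by side.**
- CIP 14.2 rests on each subject being their own control. That holds for a lead only while it is the same lead in the same position.
- Before the scan, the CIP does not treat a revised lead as continuous with the old one: revision restarts a wait of at least 45 days (8.4.4.3, Table 8). No matching analysis rule is visible after the scan.
- SAP 3.2 keeps subjects who die or withdraw in the adverse-event denominator. No equivalent is visible for effectiveness.
- SAP 3.5 limits the device-measurement summary to subjects tested at 1 month, so a withdrawn subject's immediate post-scan values would not appear there.
- The endpoint unit is the lead, but the complete-data rule in CIP 8.2.2 is worded by subject. Read literally, one missing lead value removes that subject's other leads too.

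**3. Inputs.** Leads per subject from the group definitions: 1, 2, 2 and 3. At 10 scanned subjects per group, N = 10, 20, 20 and 30 leads. Assumptions: one affected lead (or one withdrawn subject), and every other lead succeeds. Intervals are exact 95% Clopper-Pearson, the method named in SAP 2.2.2. In Groups 2 to 4 they treat leads within a subject as independent. Exempt measurements would reduce N.

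**4. One repositioned lead.** Visible reading N/N; scored as a failure (N − 1)/N; shift 100/N points.

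| Group | Visible reading | Scored as failure | Shift |
|---|---|---|---|
| 1 | 10/10 = 100% (69.2 to 100) | 9/10 = 90.0% (55.5 to 99.7) | 10.0 |
| 2 or 3 | 20/20 = 100% (83.2 to 100) | 19/20 = 95.0% (75.1 to 99.9) | 5.0 |
| 4 | 30/30 = 100% (88.4 to 100) | 29/30 = 96.7% (82.8 to 99.9) | 3.3 |

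With 15 scanned subjects per group the shifts are smaller: 14/15 = 93.3% (6.7 points), 29/30 = 96.7% (3.3 points) and 44/45 = 97.8% (2.2 points).

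**5. One withdrawn subject.** All of that subject's leads go.
- Group 1, 10 scanned: 9/9 = 100% against 9/10 = 90.0%.
- Group 1, if 10 remain evaluable after one is dropped: 10/10 = 100% against 10/11 = 90.9%, a shift of 9.1 points.
- Group 2 or 3: 20 − 2 = 18, so 18/18 = 100% against 18/20 = 90.0% (68.3 to 98.8).
- Group 4: 30 − 3 = 27, so 27/27 = 100% against 27/30 = 90.0% (73.5 to 97.9).

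The figures for Groups 2 to 4 are outer bounds, because they count every lead of the withdrawn subject as a failure.

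**6. No affected lead.** The shift is zero.

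**The case against.** The strongest objection is the redaction. A scoring rule for revised or missing leads belongs in SAP 2.1 and 2.3.2, and both are blacked out. Visible terms such as the Analysis Cohort and evaluable device data show that definitions exist there, and CIP section 11 refers the endpoint summaries to the SAP. A reader might infer that the plan has no rule for revised leads. The documents do not support that; they show only that none is visible in CIP 8.2.2 or SAP 2.9. This objection stands and limits the point.

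Second, a wholly replaced lead has no pre-scan value of its own. On a literal lead-level reading it lacks complete data and is not scored as a success. This also stands: overwriting is clear for repositioned leads and conditional for replaced ones.

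Third, the events are not hidden from the study. An MRI-related complication, as defined in Appendix A, counts in the primary safety endpoint, and each group report lists adverse events and withdrawals. A damaged lead left in place is measured and can fail. The withdrawal routes are narrow, since the Table 9 row needs three conditions together, and CIP 14.6 asks sites to attempt a final device check. All of this is right, but it does not make a proportion of 100% accurate when a scanned lead was revised for capture loss. A final check at withdrawal is also not, as such, the 1-month measurement.

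Fourth, the opening of 8.4.7.2 and the Table 9 withdrawal row need not be a serious contradiction, because the section itself refers to Table 9. That is fair; the wording still needs reconciling.

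**Conclusion.** The point holds in a limited form. Following the visible rules, a group's proportion can read 100% although a scanned lead was repositioned, or its subject withdrawn, because capture or sensing failed. Per affected repositioned lead the overstatement is 10 points in Group 1, 5 in Group 2 or 3 and 3.3 in Group 4, at 10 scanned subjects per group. For one withdrawn subject it is at most 10 points in any group.

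This rests on one assumed event, on all other leads succeeding, on the revision or loss being linked to capture or sensing failure, and on the redacted SAP text holding no rule that already settles it. A reader might go further and conclude that the proportions will be biased. The documents give no revision rate, so they do not show that; they show only that the plan's visible text does not prevent it.

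SAP 2.7 sets no success criterion and no hypothesis is tested, so no decision rule changes. This is a lower-severity point about the descriptive evidence, but worth settling before data are seen in an open-label, single-arm study.

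**What to change.** In CIP 8.2.2 and SAP 2.9, unless the redacted SAP text already does so:

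1. Do not use a post-revision measurement as the 1-month value of a scanned lead. Count a scanned lead revised, explanted or capped before 1-month testing for a capture or sensing reason as a failure of the relevant endpoint, and list each cause. The endpoints apply no test of cause to leads left in place, so this treats both alike.
2. Apply the complete-data rule per lead, to match the endpoint's unit.
3. Add one sensitivity table, labelled as a worst-case bound, counting other scanned leads without a valid 1-month value as failures. Leave out measurements the CIP exempts: RA values in atrial fibrillation or flutter (Table 2 note), RV capture at a high ventricular rate, and RV sensing at an intrinsic rate of 30 bpm or less (8.4.4.4 and 8.4.4.7.1).
4. Reconcile the opening of CIP 8.4.7.2 with the Table 9 withdrawal row.

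The cost is some wording and one table. Most of the data are already collected: "A System Revision CRF should be completed for all other types of revisions", and the Product Out of Service form records lead status. The reason for revision must be added if these forms do not hold it. The proportions may come out slightly less favourable, and the worst-case table will count some administrative losses as failures, which is why it needs that label.
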